5.5.2 Crude incidence and related risk estimates

5.5.2.1 Crude incidence and 100*(1- α)% confidence interval

For n subjects, each at risk to experience a certain event with probability π , the crude incidence is estimated as $p = x/n$, where x is the number of subjects with the event.

Absolute and relative frequencies will be displayed as well as 95% confidence interval for the relative frequency based on the score method including continuity correction (Newcombe 1998).

With z as $(1 - \alpha/2)$ -quantile of the standard normal distribution (SAS: $z=PROBIT(1-\alpha/2)$), n as total number of subjects (i.e., number of subjects in the denominator), and p as estimated crude incidence (number of subjects with event / n) it is $q = 1 - p$.

Then the lower limit is

$$L = 100 \times \max \left(0, \frac{2np + z^2 - 1 - z\sqrt{z^2 - 2 - \frac{1}{n} + 4p(nq + 1)}}{2(n + z^2)} \right)$$

And the upper limit is

$$U = 100 \times \min \left(0, \frac{2np + z^2 + 1 + z\sqrt{z^2 + 2 - \frac{1}{n} + 4p(nq - 1)}}{2(n + z^2)} \right)$$

In addition, if $L > p$ then $L = p$ and if $U < p$ then $U = p$.

If appropriate, an exact $100*(1-\alpha)\%$ confidence interval (Clopper-Pearson 1934) will be obtained by using the SAS procedure PROC FREQ with the EXACT BINOMIAL statement. However, the confidence interval derived via the score method including continuity correction will be the default in safety analysis.

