2.1 Data analysis general information

The primary endpoint analysis will be performed after all participants complete Week 16 or discontinued earlier and the final analysis will be conducted on all participant data at the time the study ends, both by Novartis. Any data analysis carried out independently by the investigator should be submitted to Novartis before publication or presentation.

Novartis will perform the analysis at Week 16 and final analysis. Statistical software SAS version 9.4 or later will be used.

Summary statistics for continuous variables will generally include the number of participants (N), minimum, lower quartile, mean, standard deviation (SD), median, upper quartile, and maximum. For binary or discrete variables, the absolute number of participants in each category and relative frequencies will be provided.

Unless otherwise specified, two-sided 95% confidence intervals will be displayed.

In case of a global health disruptive event, such as pandemic/epidemic (e.g., COVID-19), affecting the ability of the patient or the site to adhere to protocol requirements and assessments and therefore leading to a potential increase in the number of missing measurements, additional analysis populations may be defined as per the instructions and procedures outlined in Section 16.9 in the protocol.

The efficacy evaluation of secukinumab relative to placebo will generally focus on the first 16 weeks of treatment unless otherwise specified.

Data analysis will be presented by treatment group. Efficacy and safety data for the 16-week placebo-controlled period and the entire treatment period as appropriate will be presented by the following two treatment groups. Participants may be included in more than one treatment group for some analysis (e.g. exposure adjusted adverse events over the entire treatment period).

These treatment groups represent the regimens to which participants will be eligible to be randomized:

- Secukinumab 150 mg regimen
- Placebo regimen

Note that the treatment groups above for a participant may differ depending on the time period of the analysis and whether one assesses the participant for efficacy or safety.

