2.7 Safety analyses

The analysis of safety data by treatment may be provided for each Treatment Period separately and all periods combined, as appropriate. The analysis of safety data will be conducted on the Safety Set, which includes subjects who receive any study treatment. Safety analysis will be performed on treatment received or actual treatment as described below:

The actual treatment or treatment received for summaries of safety data will differ to the treatment assigned at randomization only if a subject received the wrong treatment during the entire study.

For those subjects who received not the treatment assigned at randomization, i.e. who received erroneously the wrong treatment at least once, an additional AE listing will be prepared displaying which events occurred after the treatment errors.

The safety variables to be analyzed include Adverse events (AEs), clinical laboratory tests (hematology, chemistry and urinalysis), physical examination results, ECGs, and deaths. Safety variables are to be tabulated by descriptive statistics (n, mean, median, standard deviation, minimum, and maximum; or n and percent). No formal statistical testing is planned.

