2.7.1 Adverse events (AEs)

The crude incidence of treatment-emergent adverse events (i.e., events started after the first dose of study treatment or events present prior to the first dose of study treatment but increased in severity based on preferred term and on or before last dose + 84 days) will be summarized by primary system organ class and preferred term. Confidence intervals for the crude rate will be derived as described in Section 5.5.2. In addition, exposure time-adjusted incidence rates including 95% confidence intervals will be provided for the entire treatment period (See [Section 5.5.3](#)). A graphical display of the crude incidence rates and exposure-adjusted rates will be presented for all AEs and serious AEs by system organ class.

Adverse events reported will be presented in descending frequency according to its incidence in total secukinumab group (combining all secukinumab treatment groups) starting from the most common event. Summaries (crude incidences only) will also be presented for AEs by severity and for study treatment related AEs. If a particular AE 'severity' is missing, this variable will be listed as missing and treated as missing in summaries. If a subject reported more than one adverse event with the same preferred term, the adverse event with the greatest severity will be presented. If a subject reported more than one adverse event within the same primary system organ class, the subject will be counted only once with the greatest severity at the system organ class level, where applicable.

Separate summaries will be provided for death, serious adverse event, other significant adverse events leading to discontinuation and adverse events leading to dose adjustment (including study treatment discontinuation).

A graphical display of relative frequencies within system organ classes and relative risks, as appropriate, will be presented.

Adverse events will also be reported separately by Standardized MedDRA Query (SMQ) according to MedDRA. The MedDRA version 26.1 will be used for reporting. Non-treatment emergent adverse events will be listed.

For SAEs occurred during screening a listing will be prepared for all subjects screened including screening failures.

The safety analysis that will be performed for treatment emergent AEs and on treatment labs and vital signs for each analysis period is described in Table 2-3.

Algorithms for date imputations will be provided in Programming Datasets Specification.

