The required analysis (e.g. ANCOVA) is then performed separately within each imputation dataset (as identified by variable *_imputation_*). To obtain the final result of the imputation process the analysis result from each imputation dataset needs to be combined according to Rubin’s rule as outlined below:

```
ods output parameterestimates=mi_result;  
proc mianalyze data=;  
modeleffects estimate;  
stderr estimate_se;  
run;
```

The *estimate* and *estimate_se* parameters come from the analysis model used to analyze the imputed variable within each imputation dataset (e.g., from the lsmean estimate of the treatment difference and its standard error obtained from PROC LOGISTIC or PROC MIXED)

To obtain binary response rates and confidence intervals for individual treatment groups the following process should be followed (exemplified for one visit):

```
ods output binomialprop=bin_est;  
proc freq data=;  
by treatment_imputation_;
```

```
table response / binomial (cl=wilson correct);  
run;
```

Then apply a logit transformation on the saved proportions and derive its standard error:

```
data bin_est; set bin_est;  
estimate=log(_bin_/(1-_bin_));  
estimate_se=e_bin/(_bin_*(1-_bin_));  
run;
```

[figure not shown]
The transformed binomial proportion estimates and its standard errors are then combined by applying Rubin's rules (Rubin, 1987) as described above using PROC MIANALYZE. Before presenting the combined data it needs to be transformed back as follows:

[figure not shown]
```
data mi_result; set mi_result;  
prop_est=1/(1+exp(-estimate));  
prop_lower=1/(1+exp(-lclmean));  
prop_upper=1/(1+exp(-uclmean));  
run;
```

If all responses are imputed the same as 0 (or 1) for all imputation datasets for a specific treatment or subgroup then the between-imputation-variation will be zero. The combined final response rate for the specific treatment or subgroup would be presented as seen in any of the imputed datasets together with 95% CI from Wilson's method (as obtained from PROC FREQ).

The following steps will be performed to handle special cases:

- If after imputation all responses (observed+imputed) are the same either 0 or 1 for all imputation datasets for a specific treatment or subgroup it will not be possible to perform a logit transformation and the response rate (0% or 100%) for these cases will be presented together with the 95% CI

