5.5.1.4 Analysis of binary and categorical data

5.5.1.4.1 Summary statistics for binary and categorical data

Summary statistics for discrete variables will be presented in contingency tables and will include count and frequency in each category. If applicable, confidence intervals will be derived as well based on the score method including continuity correction ([Newcombe 1998](#)):

With z as $(1-\alpha/2)$ -quantile of the standard normal distribution (SAS: $z=\text{probit}(1-\alpha/2)$), n as total number of subjects (i.e. number of subjects in the denominator), p as estimated crude incidence (number of subjects with event / n) and $q=1-p$)

Then the lower limit is

$$L = 100 \times \max \left(0, \frac{2np + z^2 - 1 - z \sqrt{z^2 - 2 - \frac{1}{n} + 4p(nq + 1)}}{2(n + z^2)} \right)$$

And the upper limit is

$$U = 100 \times \min \left(0, \frac{2np + z^2 + 1 + z \sqrt{z^2 + 2 - \frac{1}{n} + 4p(nq - 1)}}{2(n + z^2)} \right)$$

In addition, if $L > p$ then $L = p$ and if $U < p$ then $U = p$.

The placebo-adjusted response rates include 95% confidence interval will be derived using PROC FREQ with RISKDIFF statement. Note the response value should be sorted with '1' ahead of '0'. Fisher's exact test will be applied to rate events, pairwise treatment group comparisons to placebo to active controls (using PROC PREQ with FISHER statement). If appropriate, an exact $100*(1-\alpha)\%$ confidence interval (Clopper-Pearson 1934) will be obtained by using the SAS procedure PROC FREQ with the EXACT BINOMIAL statement. However, the confidence interval derived via the score method including continuity correction will be the default in safety analysis.

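### The printed upper limit of the default safety confidence interval is capped at 0 instead of 1, so it can never exceed the point estimate; the line after it mixes percent with proportion

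*SAP*

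**What the plan says.** SAP Section 5.5.2.1 estimates the crude incidence as p = x/n and states: "Absolute and relative frequencies will be displayed as well as 95% confidence interval for the relative frequency based on the score method", with continuity correction. It prints the limits as follows, with q = 1 − p:

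- L = 100 × max(0, [2np + z² − 1 − z√(z² − 2 − 1/n + 4p(nq + 1))] / [2(n + z²)])
- U = 100 × min(0, [2np + z² + 1 + z√(z² + 2 − 1/n + 4p(nq − 1))] / [2(n + z²)])

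A further line sets L to p when L > p, and sets U to p when U < p.

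Section 5.5.1.4.1 prints the same two limits and the same further line for binary and categorical summaries, where, if applicable, "confidence intervals will be derived as well based on the score method including continuity correction". Both sections state that "the confidence interval derived via the score method including continuity correction will be the default in safety analysis". Section 2.7.1 applies the method to adverse events: "Confidence intervals for the crude rate will be derived as described in Section 5.5.2". The level is set in Section 2.1: "Unless otherwise specified, two-sided 95% confidence intervals will be displayed".

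**The concern.** An upper limit for a proportion should be capped at 1, as the lower limit is floored at 0. Here both bounds are 0. A minimum of 0 and a positive number is 0, and the line that follows then lifts U to the estimate and no further.

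That line has a fault of its own. L and U carry a factor of 100, while p does not. Taken literally, it compares a percentage with a fraction and replaces one by the other.

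With about 67 participants per arm, the upper limit is the informative end of the interval for an uncommon adverse event, because it shows what rate the data cannot exclude. If the formula were programmed as printed, every crude-incidence interval would lack its upper part. An event with no cases would be shown with a 95% upper limit of 0%. The error always runs towards understating possible harm.

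**Working it through.** **Inputs.** z = 1.96 and z² = 3.841 (two-sided 95%, SAP 2.1). n = 67 per arm (134 randomized 1:1, SAP 1.1). n = 134 for any secukinumab, assuming every placebo participant switches at Week 16. The event counts are illustrative. The plan gives no figure of its own to reproduce here.

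**Step 1: are the fractions right?** The continuity-corrected score interval solves |p − π| − 1/(2n) = z√(π(1 − π)/n). Solved numerically for 7/67, this gives 0.0466 and 0.2094. The printed fractions give 4.66% and 20.94%. The fractions are correct, so the fault lies in the cap and the line after it.

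**Step 2: the cap.** In the upper fraction, 2np ≥ 0, z² + 1 > 0, the root is not negative and the denominator is positive. The fraction is therefore always positive. Over n = 2 to 200 and all x, its smallest value is 0.023. So min(0, fraction) = 0 in every case, and U is then set to p.

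**Step 3: worked example, 5/67 (p = 0.0746).**

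- Denominator: 2(67 + 3.841) = 141.68.
- Lower: (10 + 3.841 − 1 − 1.96√20.63)/141.68 = (12.84 − 8.90)/141.68 = 0.0278.
- Upper: (10 + 3.841 + 1 + 1.96√24.04)/141.68 = (14.84 + 9.61)/141.68 = 0.1726.
- Correct interval: 2.8% to 17.3%.
- With the printed cap: U = 100 × min(0, 0.1726) = 0, reset to 7.5%.

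**Step 4: size of the cap error alone.** Here L, U and p are all in percent, so the scale slip is repaired and only the cap is left as printed.

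| Events | Estimate | Printed cap | Correct |
|---|---|---|---|
| 0/67 | 0% | 0% to 0% | 0% to 6.8% |
| 1/67 | 1.5% | 0.1% to 1.5% | 0.1% to 9.1% |
| 5/67 | 7.5% | 2.8% to 7.5% | 2.8% to 17.3% |
| 10/67 | 14.9% | 7.8% to 14.9% | 7.8% to 26.2% |
| 0/134 | 0% | 0% to 0% | 0% to 3.5% |
| 5/134 | 3.7% | 1.4% to 3.7% | 1.4% to 8.9% |

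On this reading the lower limit is right, and the interval shrinks to a point only at zero events.

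**Step 5: the scale slip.** Suppose the cap is corrected to 1 but the next line is applied literally. For 5/67, L = 2.8 (percent) exceeds 0.0746 (proportion), so L becomes 0.07 and the interval reads 0.07% to 17.3%. For 67/67 the result is 1.0 to 99.86 instead of 93.2% to 100%. Correcting only the cap is not enough.

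**Step 6: both slips taken literally.** L in percent exceeds x/n in all 20,298 combinations of x and n from n = 2 to 200. The fully literal interval is therefore always the single point (p, p); for 5/67 it is (0.0746, 0.0746).

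**Step 7: can the resetting line be dropped?** No. At 0/67 the lower fraction is (2.841 − 2.649)/141.68 = 0.00136, or 0.14%, which lies above the estimate of 0. At 67/67 the upper fraction is 99.86%, below the estimate of 100%. The line is needed, on one scale.

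**The case against.** The strongest objection is that the main defect is one character in a typeset equation, sitting just below a correct max(0, …), and could be a text-conversion error. The document history also records that Amendment 1 corrected this expression in 5.5.2.1. Against this, the same 0 stands in two separate sections, and the fractions around it check out numerically, so a misreading is unlikely. The log entry does not settle what the current text says. A look at the two equations in the PDF will.

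Second, the table in Step 4 is not the fully literal result, because it repairs the scale slip first. That is true and is stated there. The literal result is worse, a single point in every case.

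Third, the factor of 100 can be seen as display scaling that any programmer would handle. That is fair as a forecast of what a programmer would do, but the line as written is still wrong and is easily corrected together with the cap.

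Fourth, the practical effect may be nil. The method is named and referenced, an exact alternative is offered, and intervals that stop at the estimate in every row would be noticed when output is reviewed. Safety is descriptive: "No formal statistical testing is planned". This stands as a limit on the weight of the point. It is not a reason to leave a wrong formula in place for the default interval, since anyone checking output against the SAP would have to depart from it.

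**Conclusion.** The formula is wrong as printed in both sections. The cap of 0 removes the whole upper part of the interval, and the mixed scale in the next line is a second, independent error. At n = 67 the upper limit falls from 17.3% to 7.5% for 5 events and from 6.8% to 0% for none.

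The scope is limited to crude adverse-event incidences and, where applicable, binary and categorical summaries. The primary ASAS40 analysis uses marginal standardization from the logistic model, and the placebo-adjusted rates use PROC FREQ with RISKDIFF; neither depends on this formula. No sample size, power or error rate changes. The figures assume 67 per arm and, for n = 134, that every placebo participant switches. Whether any output is wrong depends on the program, which the documents do not show. The text should be fixed; the point does not threaten the trial's main conclusion.

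**What to change.** In SAP Sections 5.5.1.4.1 and 5.5.2.1:

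1. Replace min(0, …) by min(1, …) in the upper limit.
2. Put the resetting line on one scale: if L > 100p, set L = 100p; if U < 100p, set U = 100p. Equivalently, apply it before multiplying by 100.

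Alternatively, delete the printed formula and refer to the SAS option that Section 5.5.1.2.1 already uses: "table response / binomial (cl=wilson correct").

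Then confirm that the safety program does not implement the printed lines; 0/67 should return 0% to 6.8% and 5/67 should return 2.8% to 17.3%. The cost is a two-line correction in each of two sections and one program check. No planned analysis or trial procedure changes.

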5.5.2.2 Odds ratio and $100*(1-\alpha)\%$ confidence interval

For an investigational drug group with n_1 subjects at risk, independent from the control group (e.g., placebo or comparator) with n_0 subjects at risk, of whom x_1 and x_0 experience a certain event with probability π_1 and π_0 respectively, the odds ratio is estimated as $\frac{p_1/(1-p_1)}{p_0/(1-p_0)}$ with $p_1 = x_1/n_1$ and $p_0 = x_0/n_0$. A conditional exact $100*(1-\alpha)\%$ confidence interval can be obtained by using the SAS procedure PROC FREQ with statement EXACT OR. However, to be able to adjust for covariates odds ratios will primarily be obtained from PROC LOGISTIC.

5.5.2.3 Risk difference and $100*(1-\alpha)\%$ confidence interval

For an investigational drug group with n_1 subjects at risk, independent from the control group (e.g., placebo or comparator) with n_0 subjects at risk, of whom x_1 and x_0 experience a certain event, the risk difference is estimated as $p_1 - p_0$ with $p_1 = x_1/n_1$ and $p_0 = x_0/n_0$.

Exact unconditional confidence limits for the risk difference can be obtained with SAS procedure PROC FREQ and option RISKDIFF in the TABLES statement, specifying the RISKDIFF option also in the EXACT statement.

5.5.3 Exposure adjusted incidence rate and related risk estimates

5.5.3.1 Exposure adjusted incidence rate and 100*(1- α)% confidence interval

It will be assumed that for each of n subjects in a clinical trial the time t_j ($j = 1, \dots, n$) to the first occurrence of a certain event is observed, or if the event was not experienced, the (censored) time to the end of the observation period. The sequence of first occurrences of an event will be modeled to follow approximately a Poisson process with constant intensity θ . The rate parameter θ will be estimated as $\lambda = D/T$, where $T = \sum_{j=1}^n t_j$ and D is the number of subjects with at least one event. Conditionally on T , an exact $100*(1-\alpha)\%$ confidence interval for a Poisson variable with parameter θT and observed value D can be obtained based on (Garwood, 1936), from which an exact $100*(1-\alpha)\%$ confidence interval for D/T will be derived as follows (Sahai, 1993; Ulm, 1990):

$$\text{Lower confidence limit } L = \frac{0.5c_{\alpha/2,2D}}{T} \text{ for } D > 0, 0 \text{ otherwise,}$$

$$\text{Upper confidence limit } U = \frac{0.5c_{\alpha/2,2D+2}}{T}$$

Where $c_{\alpha,k}$ is the α th quantile of the Chi-square distribution with k degrees of freedom.

The example below shows how this should be handled for cases where subjects switch treatment. In particular for summarizing 'Any AIN' as a group, one should take into consideration the sequence of treatments while calculating exposure time for subjects.

Table 5-3 Examples for calculating exposure time for incidence rates (IR)

| 1st treatment | 1st exposure | 2nd treatment | 2nd exposure | Event days (in terms of study day) | Exposure for IR |
|---------------|--------------|---------------|--------------|--|---|
| Placebo | 100 days | 150 mg | 200 days | 50 (1st trt) 110 (10 days into 2nd trt) | Placebo: 50 days (event) 150 mg: 10 days (event) Any AIN: 10 days (event) |

6 References

Garwood, F. (1936) Fiducial limits for the Poisson distribution. *Biometrika*; 46: 441-453.

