Table 2-3 Overview of analysis on some safety endpoints

| Analysis period | AEs & SAEs | AEs-SMQ | AEs by severity | study drug related AEs | Notables for (vitals/ECG), lab criteria | Risk |
|------------------|--|-------------------------------|-------------------|------------------------|---|--|
| Day 1 – Week 16 | • crude incidence | • crude incidence | • crude incidence | • crude incidence | • crude incidence | • crude incidence |
| Entire Treatment | • crude incidence • exp.time adjusted incidence | • exp.time adjusted incidence | • crude incidence | • crude incidence | • crude incidence | • crude incidence • exp.time adjusted incidence |

* Exposure-adjusted incidence rates will be done for the following:

- At the PSOC for AE and SAE
- At the PT level for common AEs, which is defined as at least 2% of the patients in the secukinumab during the initial treatment period (i.e. up to week 16) or events that had an incidence rate of at least 5.0 cases per 100 subject-years in the combined secukinumab groups during the entire treatment period
- At Level 1 for Risks and SMQ analyses

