2.7.1.1 Adverse events of special interest / grouping of AEs

Safety topics of interest, including risks defined in the Risk Management Plan (RMP) or other topics of interest for signal detection or routine safety analysis can be retrieved via the RMP flag and SPP flag. The crude incidence and exposure-adjusted incidence rates for the safety topics of interest will be summarized.

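### The exact Poisson interval in SAP 5.5.3.1 uses the lower-tail chi-square quantile in both limits, so at 95% the printed upper limit lies below the rate whenever there is at least one event

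*SAP*

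**What the plan says.** SAP 5.5.3.1 estimates the rate as D/T, where D counts participants with at least one event and T sums the time to first event or to censoring. It says that an exact 100(1 − alpha)% interval will follow from the Garwood interval for a Poisson count. The two printed limits are:

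- lower: "L = \frac{0.5c_{\alpha/2,2D}}{T" (0 when D = 0)
- upper: "U = \frac{0.5c_{\alpha/2,2D+2}}{T"

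The symbol c with subscripts (alpha, k) is defined as the alpha-th "quantile of the Chi-square distribution with" k degrees of freedom. SAP 2.1 sets the level: "Unless otherwise specified, two-sided 95% confidence intervals will be displayed".

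The interval is planned output. SAP 2.7.1 promises "exposure time-adjusted incidence rates including 95% confidence intervals will be provided for the entire treatment period". The footnote to Table 2-3 applies exposure-adjusted rates to AEs and SAEs by primary system organ class, to common preferred terms, and to risks and SMQs at Level 1. One route to being a common preferred term is "events that had an incidence rate of at least 5.0 cases per 100 subject-years in the combined secukinumab groups". For safety topics, SAP 2.7.1.1 adds: "The crude incidence and exposure-adjusted incidence rates for the safety topics of interest will be summarized".

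**The concern.** A two-sided interval takes one quantile from each tail. Here both limits index the same lower-tail quantile, and only the degrees of freedom differ (2D against 2D+2). The upper limit is then simply the lower limit for one more event, which cannot bound the rate from above.

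If the formula was coded as printed, every exposure-adjusted rate with at least one event would appear with an interval that excludes its own estimate. That fault would be visible in a table. The D = 0 case is harder to notice: the interval contains the estimate of zero and looks orderly, but its upper limit is far too small. For a rare risk with no observed events, the upper limit is the informative figure.

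**Working it through.** The SAP gives a formula but no worked value, so there is no figure of its own to reproduce. I evaluated the printed limits and compared them with the exact Poisson limits.

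**Inputs.** From SAP 2.1, alpha = 0.05, so alpha/2 = 0.025. From SAP 5.5.3.1, the two limits and the definition of c. Limits below are in event counts; divide by T for the rate.

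**Step 1. Formulas.** Write q(p, k) for the p-th quantile of chi-square with k degrees of freedom.

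- Lower, printed and correct: 0.5 q(0.025, 2D)
- Upper, printed: 0.5 q(0.025, 2D+2)
- Upper, exact: 0.5 q(0.975, 2D+2)

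**Step 2. Values.**

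| D | Lower | Upper as printed | Upper, exact |
|---|---|---|---|
| 0 | 0 | 0.025 | 3.69 |
| 1 | 0.025 | 0.24 | 5.57 |
| 5 | 1.62 | 2.20 | 11.67 |
| 10 | 4.80 | 5.49 | 18.39 |
| 20 | 12.22 | 13.00 | 30.89 |
| 50 | 37.11 | 37.97 | 65.92 |

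At D = 0 the unrounded values are 0.02532 and 3.6889, a ratio of about 146.

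**Step 3. Why the printed upper limit is always below D.** Half a chi-square variable with 2D+2 degrees of freedom is at most D with probability P(Poisson(D) ≥ D+1). The printed upper limit is therefore below D exactly when alpha/2 is smaller than that probability. The probability is 0.264 at D = 1, its smallest value over D = 1 to 100,000, and rises toward 0.5. Since 0.025 < 0.264, the printed limit is below D throughout. Direct evaluation confirmed this for every D from 1 to 100,000, which includes every possible count up to the planned 134 participants. The result holds for any alpha below about 2 × 0.264 = 0.528, so at every usual confidence level.

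**Step 4. Coverage.** The printed upper limit for D equals the lower limit for D+1, so the printed intervals abut and only one value of D covers a given expected count. At an expected count of 1 that value is D = 3 (0.619 to 1.090), and P(Poisson(1) = 3) = 6.1%.

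| Expected count | Coverage as printed | Coverage, exact interval |
|---|---|---|
| 1 | 6.1% | 98.1% |
| 5 | 1.8% | 98.0% |
| 10 | 1.3% | 97.5% |

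**Step 5. Other reading of c.** Taking c as an upper-tail quantile contradicts the printed definition and moves the error to the lower limit: 3.69 at D = 1, 10.24 at D = 5 and 17.08 at D = 10, each above D. No single convention makes both limits right.

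**Step 6. At the SAP's threshold of 5.0 per 100 subject-years.** T is not given, so I assume 100 to 133.5 subject-years on any secukinumab. The top of the range takes 67 participants on secukinumab for 60 weeks and 67 for the 44 weeks after the Week 16 switch: (67 × 60 × 7 + 67 × 44 × 7)/365.25 = 133.5. Stopping the clock at first events would lower it.

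| T | D | Rate per 100 | Upper as printed | Upper, exact |
|---|---|---|---|---|
| 100 | 5 | 5.0 | 2.20 | 11.67 |
| 133.5 | 7 | 5.24 | 2.59 | 10.80 |

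An event qualifying because its rate reached 5.0 would show an upper limit of roughly 2.2 to 2.6.

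**The case against.** The strongest reply is that the section names the right method. It calls the interval exact and cites Garwood, so a statistician following the text rather than the symbols would program the correct limits. An upper limit below the estimate in every row with an event would also be caught when the tables are first read. That is fair: the coverage figures describe the formula as printed, and nothing shows that the program uses it. The check would still be needed for D = 0, where the error is not obvious. A citation also does not correct an explicit formula that contradicts it.

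A second reply is that a 1 − may have dropped out of the subscript when the PDF was converted to text. Small subscripts inside displayed fractions are vulnerable, and the displayed upper limits in SAP 5.5.1.4.1 and 5.5.2.1 also show an odd symbol (a minimum taken with 0). Against this, the 0.5 and the 2D+2 in the same expression are intact, and 1 − alpha appears correctly elsewhere in the section. The possibility cannot be fully excluded.

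Third, the consequence is limited. SAP 2.7 states: "No formal statistical testing is planned". Table 2-3 gives crude incidence beside the exposure-adjusted rate for AEs, SAEs and risks; only SMQs over the entire treatment period have the exposure-adjusted rate alone. SAP 2.7.1 promises intervals for the AE rates. Applying them to risks and SMQs is my inference from the general method in 5.5.3.1. These points limit the importance of the error but do not make the formula right.

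**Conclusion.** The concern holds. As printed, SAP 5.5.3.1 does not give the exact interval it announces. The lower limit is correct and the upper limit uses the wrong tail, and nothing elsewhere in the SAP or protocol supplies a different formula. The error is large wherever it applies: a nominal 95% interval with single-digit coverage.

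This conclusion rests on the printed definition of c, on alpha = 0.05, and on the subscript being the same on the released SAP page. Any effect on reported results also depends on the printed index having been coded. The point estimates D/T, the crude-incidence intervals (a separate formula), the ASAS40 primary analysis and the sample size do not depend on it.

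**What to change.** Confirm the subscript on the released SAP page. If it reads as above, change the upper limit to 0.5 × c(1 − alpha/2, 2D+2)/T and leave the lower limit and the definition of c as they are.

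Then check the program for the exposure-adjusted rates. Two test values at 95% are enough: the upper limit should be 3.69/T for D = 0 and 11.67/T for D = 5. Rerun the affected tables only if the program fails.

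The cost is a one-symbol correction and a short program check. There is precedent: the SAP's document history records a corrected confidence-interval expression for crude incidence in Amendment 1.
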